Analyses of endpoints will be performed based on evaluations obtained on days 0, 28±2, 56±4 and 28±4 days after discontinuation of study treatment. Details of analyses will be presented in the Statistical Analysis Plan finalized before Database Lock.

Sample size calculation

Sample size was calculated by assuming both for severity and frequency a mean difference from baseline SANDE scores of -30±20 in the rhNGF groups versus -20±20 in vehicle group (80% power, alpha =0.05; 2-sided test), considering that the active compound has already proven safe

and effective in dry eye patients. The sample size has been calculated based on a 2:1 randomization scheme by the following formula:

$$n_1 = (0.5) \times n \times (1 + k)$$

$$n_2 = (0.5) \times n \times (1 + (1/k))$$

With n_1 = active treatment, n_2 = vehicle, $n = 63$, and $k = n_1/n_2 = 2/1=2$. Therefore, $n_1 = 94.5$ and $n_2 = 47.25$. Assuming a 5% dropout rate, a total of 100 patients will be enrolled in the active arm, and 50 in the vehicle arm.

Study procedures				
Study procedures	Baseline Visit Day 0	Week 4^a	Week 8^b	Follow-up Visit Week 12 or early termination^b
Informed Consent	X			
Inclusion/Exclusion Criteria	X			
Urine Pregnancy Test	X		X	
Randomization	X			
Demographics	X			
Ocular and General Medical History	X			
Previous and Concomitant Ocular And Systemic Medications	X	X	X	X
Frequency of Artificial Tear Use	X			X
Record Adverse Events (AEs)	X	X	X	X
Verify Patient Study Medication Dosing Compliance		X	X	
SANDE ^c questionnaire	X	X	X	X
Best Corrected Distance Visual Acuity (BCDVA)	X	X	X	X
Schirmer test I (without anesthesia)	X		X	
External Ocular Examination	X	X	X	X
Slit-lamp Examination (SLE)	X	X	X	X
Fluorescein and lissamine green staining (NEI scale)	X	X	X	X
Tear Film Break-up Time (TFBUT)	X	X	X	X
InflammaDry (MMP-9)	X		X	
Study Drug Dispensation	X	X		

a.) Visit window of ± 2 days; b.) Visit window of ± 4 days; c.) SANDE - Symptom Assessment In Dry Eye

TABLE OF CONTENTS

	Page	
1	INTRODUCTION	16
1.1	Background Information	16
1.1.1	Nerve growth factor - overview	16
1.1.2	Chemical and formulation data	16
1.1.3	Rationale for rhNGF therapy in patients with dry eye	16
1.1.4	Previous experience in humans with rhNGF	17
1.2	Study Rationale	18
1.2.1	Dose and Schedule Rationale	18
1.3	Risks and benefits	19
2	STUDY OBJECTIVES	20
2.1	Primary endpoint	20
2.2	Secondary endpoints	20
2.3	Exploratory endpoint	20
2.4	Safety endpoint	20
3	CLINICAL SUPPLIES	21
3.1	Treatment	21

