6.1 Study visits and procedures

Each study patient will undergo 4 visits.

Maximum study duration will be 84 days. A written informed consent will be obtained before any study assessment or procedure.

The first patient first visit (FSFV) is defined as the 1st visit performed at the clinical center by the 1st screened patient. The “last patient, last visit” (LSLV) is defined as the last visit performed at the clinical center (or the telephone follow-up, if applicable) by the last patient (i.e., the last visit foreseen by the study protocol), independently of whether the patient completed or withdrew from the study.

The following phases, visits and procedures will be performed:

➤ Interventional phase

- Baseline Visit - Day 0
- Week 4 Visit - Day 28 ± 2
- Week 8 Visit - Day 56 ± 4

➤ Follow-up phase

- Week 12 Follow-up Visit - Day 84 ± 4 / Early Termination Visit (ETV): In case of early discontinuation, discontinued patients will undergo an early termination visit (ETV)

	Day	Procedures/Assessments

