Week 12 Visit Final visit or early termination visit (ETV)	Day 84 ± 4	
The final visit is defined as the visit performed 28 ± 2 days after the last IMP administration (i.e., at day 84 ± 4). In case of premature study discontinuation, patients will undergo an early termination visit (ETV).
 
The following procedures will be performed (the below order is not mandatory):
 
 ➤ Medical and surgical history/current medical conditions ➤ Prior/concomitant medications ➤ AE monitoring ➤ Ocular examination of both eyes: 
 1. Assessment by SANDE questionnaire 2. Assessment of best corrected distance visual acuity (BCDVA) 3. Slit-lamp examination (SLE) to assess the Eyelid - Meibomian glands, Eyelid – Erythema, Eyelid - Edema Lashes, Conjunctiva Erythema, Lens, Iris, Anterior Chamber 4. External Ocular Examination 5. Tear Film Break-up Time (TFBUT) 6. Ocular surface staining (NEI score - Fluorescein and Lissamine green) ➤ Frequency of patient’s own artificial tear use during 4 weeks of FU (to be reported in eCRF)

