8.1 Randomization

Eligible patients will be randomized 2:1 to either rhNGF eye drops 20 µg/ml (100 patients) or vehicle solution (50 patients).

Each randomized patient will be allocated with randomization number to a consecutive list of starting with 1001 onwards.

Drop outs after randomization will not be replaced.

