10.2 Sample size and power considerations

Sample size was calculated by assuming both for severity and frequency a mean difference from baseline SANDE score of -30 ± 20 in the rhNGF groups versus -20 ± 20 in vehicle group (80% power, $\alpha = 0.05$; 2-sided t-test), considering that the active comparator has already proven safe and effective in dry eye patients. Therefore, the sample size has been calculated based on a 2:1 randomization scheme by the following formula:

$$n_1 = (0.5) \times n \times (1 + k)$$

$$n_2 = (0.5) \times n \times (1 + (1/k))$$

With n_1 = active treatment, n_2 = vehicle, $n = 63$, and $k = n_1/n_2 = 2/1=2$. Therefore, $n_1 = 94.5$ and $n_2 = 47.25$. Assuming a 5% dropout rate, a total of 100 patients will be enrolled in the active arm, and 50 in the vehicle arm.

Since this is an exploratory study, no adjustment has been made for multiplicity of SANDE parameters, neither has it been taken into account that the actual analysis will be descriptive only.

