13.4.1 Primary reason for discontinuation

- **Adverse event (AE):** Any significant AE that, in the opinion of the Investigator or concerned patient, is not compatible with study continuation. For the definition of AE, please refer to § 11.2.
- **Death:** the absence of life or state of being dead
- **Lack of efficacy:** the lack of expected or desired effect related to a therapy
- **Lost to follow-up:** the loss or lack of continuation of a patient to follow-up
- **Non-compliance with study drug:** an indication that a patient has not agreed with or followed the instructions related to the study medication
- **Physician decision:** a position, opinion or judgment reached after consideration by a physician with reference to the patient
- **Pregnancy:** pregnancy is the state or condition of having a developing embryo or fetus in the body (uterus), after union of an ovum and spermatozoon, during the period from conception to birth (please see § 11.10)
- **Protocol violation:** an event or decision that stands in contrast to the guidelines set out by the protocol
- **Study terminated by the Sponsor:** an indication that a clinical study was stopped by its Sponsor
- **withdrawal by patient:** study discontinuation requested by a patient for whatever reason
- **other:** different than the ones previously specified.

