13.5 Study termination

The study will be considered terminated at the date of the last visit of the last patient or upon completion of any follow-up procedure described in the protocol. The Investigator and the Sponsor have the right to discontinue the study at any time for reasonable medical and/or administrative reasons. As far as possible, this should occur after mutual consultation. Reasons for discontinuation have to be documented appropriately. In this event, no further patients will receive doses of the study drugs, and patients already having received a dose of study drug will not receive any further doses of the study IMP but will undergo all safety assessments scheduled after the last dose of study drug, up to and including the end of study examination.

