This is defined as a TEAE (as defined above) with a start date on or after the Week 8 Visit. It will be identified, if eCRF question 'Did the event occurred:' was answered with 'During Follow-Up period'.

For listing purposes, treatment day of onset of AE will be presented according to the definition given in section 8.1.

Missing Codes or Incomplete AE start dates:

In the event that coding information will not be available for a specific AE, the event will be presented as 'Uncodable Event'). However, for final TLFs it is anticipated that all events are coded.

If the eCRF question 'Did the event occur:' was not answered, AEs will be classified to subclass Non-TEAEs, TEAE in the Treatment Period or TEAE in the Follow-up Period based on the AE onset date utilizing the definitions given above (including those for ocular events in untreated eyes). If this is not possible, the event will be classified as TEAE in the Treatment Period.

Missing and/or incomplete AE onset dates will be imputed for calculating relative start and stop days only. Dates will be listed as missing/incomplete [with "-" replacing missing information] but the onset Day listed between square brackets to denote it was calculated based on missing data (i.e. [1]).

Missing and/or incomplete dates will be imputed in a manner that assumes the worst case scenario:

- For a missing start day (but month and year is available), onset is assumed on the first day of the respective month.
- For a missing start month (but year is available), onset is assumed on 1st January of the respective year.
- For a completely missing start date, no imputation will be performed.

If for Non-TEAEs this procedure results in an onset date before date of informed consent, informed consent date will be used.

If for TEAEs during treatment period this procedure results in an onset date before date of first study treatment, date of first study treatment will be used.

If for TEAEs in the Follow-Up period this procedure results in an onset date before date of Week 8 visit, date of Week 8 visit will be used.

Best Corrected Visual Acuity (BCDVA)

Best-corrected visual acuity is measured at all trial visits using standard charts, lighting, and procedures. All eyes must be tested at 4 meters first, even if the refraction was performed at 1 meter. When a patient cannot read at least 20 letters on the chart at 4 meters, the patient is tested at 1 meter.

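### The protocol contradicts itself on visits after early stopping, and on neither reading is a patient who leaves early asked back at Day 56

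*Protocol*

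**What the plan says.** Two sets of visit rules stand side by side in the protocol.

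- **One exit visit in the Week 12 slot.** The visit list in 6.1 states "In case of early discontinuation, discontinued patients will undergo an early termination visit (ETV", on the line for Week 12. The visit table in 6.1 repeats it in the Week 12 row: "In case of premature study discontinuation, patients will undergo an early termination visit (ETV". The synopsis schedule has one column for Week 12 and early termination together. Section 13.4.2 asks for a single final visit as far as possible and names nothing after it.
- **Early exit in the Week 8 slot, then an off-drug visit.** The synopsis (Study Design and Methodology) and section 4.1 list Week 8 and early exit as alternatives, followed by a visit 4 weeks after treatment ends.

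Section 13.4 covers stopping treatment and stopping observation in one rule. The reasons in 13.4.1 include lack of efficacy and non-compliance with study drug, the latter being "an indication that a patient has not agreed with or followed the instructions related to the study medication". If the whole study is terminated, 13.5 is explicit: patients already dosed "will undergo all safety assessments scheduled after the last dose of study drug, up to and including the end of study examination". There is no equivalent sentence for one patient who stops.

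SAP 8.2.7 fills a missing Week 8 SANDE by LOCF and imputes neither Schirmer nor MMP-9. SAP 8.1, Table 2, has no row for the early termination visit and counts Week 12 from the last intake. SAP 8.2.8 separates AEs that end treatment from AEs that end study participation. Of follow-up TEAEs it says: "This is defined as a TEAE (as defined above) with a start date on or after the Week 8 Visit".

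**The concern.** The primary question is the SANDE difference at 8 weeks, and the design includes 4 weeks off drug. Someone who stops drug because of an AE, lack of efficacy or non-compliance has not necessarily refused to be observed. Yet the protocol defines no separate path for a patient who is off drug but still willing to attend.

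Three things are at stake:

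- The Week 8 value in these patients is carried from an earlier date.
- A site that follows the visit table may omit both the scheduled off-drug eye examination and the visit at which new events would be asked about.
- The SAP does not say where exit values belong.

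Data not collected at Day 56 or after the last dose cannot be recovered by analysis.

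**Working it through.** **1. The two rules, item by item, for a patient who leaves before Day 56**

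| Item | 6.1, synopsis schedule, 13.4.2 | Synopsis design text, 4.1 |
|---|---|---|
| Exit visit | Yes, Week 12 slot | Yes, Week 8 slot |
| Return at Day 56 | Not asked | Not asked |
| Visit 4 weeks off drug | Can be omitted | Kept |
| SANDE, staining, TFBUT at exit | Listed | Procedures not listed in that text |
| Schirmer, MMP-9 at exit | Not listed | Possible if Week 8 procedures apply; not stated |

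The absence of a Day 56 return is common to both. The loss of the off-drug visit is not.

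**2. Two anchors for the final visit.** The visit table in 6.1 places the final visit 28 days after the last dose and also at Day 84. These agree only if the last dose is on Day 56 (56 + 28 = 84). For a last dose on Day 20, the off-drug visit falls on Day 48, before Week 8. SAP Table 2 would accept it as Week 12, because 28 lies in the window of 24 to 32 days after last intake. The SAP does not say whether that value, or the exit value, may fill Week 8 by LOCF or enter the Week 12 ANCOVA.

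**3. The plan's sample size.** Inputs from Protocol 10.2: difference 10, SD 20, power 80%, two-sided alpha 0.05, ratio 2:1, 5% dropout.

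- Per group at 1:1: 2 × [20 × (1.960 + 0.842)/10]² ≈ 62.8, rounded up to 63.
- At 2:1: 0.5 × 63 × 3 = 94.5 and 0.5 × 63 × 1.5 = 47.25. Divided by 0.95 and rounded up, these give 100 and 50.
- SAP 4.6 gives 96 + 48; the t-test power there is 0.802. The plan's figures reproduce.

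**4. Patients affected.** Protocol 10.2: "Assuming a 5% dropout rate, a total of 100 patients will be enrolled in the active arm, and 50 in the vehicle arm".

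- 0.05 × 100 = 5 on rhNGF and 0.05 × 50 = 2.5 on vehicle, so 7.5 of 150.
- Off-drug time at risk of going unobserved: 7.5 × 28 = 210 patient-days. This is a ceiling: it assumes that all dropouts stop before Week 8 and none has the visit kept by section 4.1.

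**5. Effect on the primary comparison.** Let p be the share stopping in an arm and D the gap in SANDE points between the carried value and the unobserved Week 8 value. The shift in the treatment difference is p(rhNGF) × D(rhNGF) − p(vehicle) × D(vehicle). The documents do not give D; 10 to 30 points is assumed, with D equal in both arms except where stated.

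| Stopping, rhNGF vs vehicle | Shift in difference |
|---|---|
| 5% vs 5% | 0 (each arm moves 0.5 to 1.5) |
| 8% vs 0% | 0.8 to 2.4 |
| 10% vs 5% | 0.5 to 1.5 |
| 15% vs 5% | 0.10 × 10 = 1 to 0.10 × 30 = 3 |

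If D is 30 in one arm and 10 in the other, even 5% in both arms shifts the difference by 0.05 × 20 = 1.0 point. If stoppers are worse at Day 56 than their carried value, more stopping on rhNGF flatters rhNGF, and more stopping on vehicle does the reverse.

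**6. Power.** With 100 + 50 values, power is 0.818; with 95 + 47.5 it is 0.798. That 2-point loss would apply if stoppers gave no value. For SANDE it is an upper bound, because LOCF supplies a value wherever a post-baseline one exists.

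**7. Follow-up TEAEs.** SAP 8.2.8 first uses the period ticked on the eCRF. If that is blank, it uses onset relative to the Week 8 visit, and if that fails, the event counts as treatment-period. For a patient with no Week 8 visit the date rule has no anchor. An off-drug event with a blank tick therefore goes into the treatment-period table.

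**The case against.** The case against is substantial, and several stronger readings fail on it.

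- **That the off-drug visit is abolished.** The synopsis and section 4.1 keep it, and SAP Table 2 counts the last visit from last intake. Its loss is one reading of conflicting text.
- **That the primary value is lost.** SANDE is done at the exit visit, and the endpoint is openly defined with LOCF. Only a patient with no post-baseline SANDE has no value. SAP 8.2.7 already uses an observed Week 8 score when there is one, so no change is needed there.
- **That early stoppers can never contribute a follow-up TEAE.** The eCRF tick comes first and can be set for them. The safety endpoint counts all TEAEs, so a reported event is not dropped; only its period may be wrong.
- **That the losses fall on those doing worst.** Section 13.4.1 also lists neutral reasons, and no document gives rates by reason.

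It can also be said that a patient who stops drug but stays in the study falls under the four-visit rule of 6.1, since the visit table ties the exit visit to leaving the study. That is a fair reading, but the visit list in 6.1 speaks only of early discontinuation and 13.4 merges the two kinds of stopping, so a site could decide either way.

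Some off-drug safety information survives. Protocol 11.9 follows AEs to outcome or for 10 days after the final visit, and 11.11 follows AE withdrawals to resolution or as the medical monitor instructs. These provisions follow known events; they do not schedule an examination or a search for new ones. Finally, some of the 5% will be lost to follow-up or withdraw consent, and no wording recovers them.

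**Conclusion.** The point holds in this form: the protocol gives conflicting visit rules after early stopping, no rule brings back at Day 56 a patient who has left, and the SAP does not place the exit visit. Under the visit table, Schirmer and MMP-9 at Week 8 are missing and the off-drug examination can be omitted.

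The size is modest at the planned dropout: at most 7 to 8 of 150 patients, and no shift in the treatment difference if stopping and error are equal between arms. It becomes material, at 1 to 3 of the planned 10 points, only with unbalanced stopping such as 15% versus 5%. Those rates and the 10 to 30 point gap are assumptions. The trial is declared exploratory with unadjusted tests. This is a change that should be made because it is cheap; it does not invalidate the design.

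**What to change.** **Protocol.** Reconcile the synopsis design text and 4.1 with the synopsis schedule, 6.1 and 13.4.2. In 13.4, separate stopping study drug from leaving the study. Unless consent is withdrawn, still ask a patient who has stopped drug to attend the already-defined Week 8 assessments and the off-drug safety visit, counted from the last dose. The rules for stopping treatment are not changed.

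**SAP.** Add the early termination visit to Table 2. State whether exit and off-drug values may enter LOCF for Week 8 and the Week 12 analysis. Where there is no Week 8 visit, start the follow-up AE period from the last dose.

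**Cost.** Wording in both documents, and one or two already-defined visits for about 7 to 8 patients at a single centre. For a last dose on Day 28 the two visits coincide (28 + 28 = 56). The downside is that Week 8 values in these patients may reflect artificial tears or other treatment begun after stopping. Concomitant medication is already recorded, so this can be described when the results are read.

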7 DESCRIPTION OF SPECIFIC PROCEDURES

7.1 Ophthalmological Evaluations

Ocular evaluations will be performed on both eyes. The assessment will be performed at Day 0 Baseline Visit, Week 4 Visit, Week 8 Visit and Week 12 Visit. The study eye will be the worse eye determined at Day 0 Baseline Visit (the right eye if both eyes are equally worse). The ophthalmological assessment will include:

7.1.1 External Ocular Examination

External Ocular Examination assesses the motility of the extraocular muscles and the appearance and function of the eyelids before the instillation of any dilating or anesthetic eye drops.

7.1.2 Symptom Assessment in Dry Eye (SANDE):

The Symptom Assessment in Dry Eye (SANDE) questionnaire is a short questionnaire to evaluate both dry eye intensity and frequency by using a 100 mm VAS. The patient symptoms of ocular dryness and/or irritation will be quantified on the scale based on two questions that assess both severity and frequency of symptoms. A VAS is a measurement instrument that tries to measure a characteristic or attitude that is believed to range across a continuum of values and cannot easily be directly measured. For example, the amount of irritation that a patient feels ranges across a continuum from none to an extreme amount of irritation. From the patient's perspective this spectrum appears continuous (i.e. their irritation does not take discrete jumps, as a categorization of none, mild, moderate and severe would suggest). It was to capture this idea of an underlying continuum that the VAS was devised.

For the assessment, the patients mark on the 100 mm VAS line the point that they feel represents their perception of their current state. The VAS score is determined by measuring in millimeters from the left hand end of the line to the point that the patient marks. The SANDE scores will be then evaluated for the 2 questions severity (0-100) and frequency (0-100).

7.1.3 Best corrected distance visual acuity (BCDVA):

Refraction and visual acuity measurements will be performed for all patients by trained vision examiners only. The name and certification number of the vision examiner should be documented in the patient's visual acuity (VA) worksheet (provided by the Sponsor) at each visit. Refraction should be conducted prior to visual acuity testing to obtain best-corrected vision as described below. Best-corrected visual acuity is measured at all trial visits using standard charts, lighting, and procedures. Best correction is determined by careful refraction at that visit according to the standard protocol for refraction as described below.

Equipment

Refraction equipment required includes:

- Retroilluminated Light box and ETDRS 4 meter distance acuity chart set
- Trial lens frames
- Trial lens set with plus or minus cylinder lenses
- Jackson cross-cylinders of 0.25, 0.50, and 1.00 diopters
- Pinhole occluder
- Tissues or eye pads and tape
- A 1 meter rigid measuring stick

Visual acuity charts: Chart 1 is used for testing the visual acuity of the RIGHT eye; Chart 2 for testing the LEFT eye; and Chart R (or 3) for refraction only. Patients should not be allowed to see any of the charts before the examination.

A distance of 4 meters is required between the patient's eyes and the visual acuity chart. With the box light off, not more than 15 foot-candles of light (161.4 Lux) should fall on the center of the chart. To measure the amount of light, the room is set up for visual acuity testing, but with the box light off. The light meter is placed at the fourth line from the top of the chart, with its back against the chart and the reading is taken. If more than one line available for testing visual acuity, the visual acuity of an individual patient should be measured in the same line at each visit, if possible. If different lines are used to test visual acuity, they must each meet the same standards.

Retroilluminated ETDRS charts are used in this trial. The illuminator box will be either wall-mounted or mounted on a stand. The light box should be mounted at a height such that the top of the third row letter is 49 + 2 inches from the floor.

The visual acuity light box is equipped with two General Electric 20-watt fluorescent tubes and ballast. Each tube is partly covered by a 14-inch fenestrated sleeve, which is centered on the tube and open in the back. This serves as a "baffle" to produce even illumination over the testing chart. Because the illumination of fluorescent tubes diminishes by 5 percent during the first 100 hours and by another 5 percent during the next 2000 hours, new tubes should be kept on for 4 days (96 hours) continuously, and should be replaced once a year.

A sticker should be placed on the back of the light box, indicating the date when the present tubes were installed. A spare set of burned in bulbs should be available on site.

Detailed instructions for VA assessment

As a reminder, Charts 1, 2 and R (or 3) are used for testing the right eye, left eye, and refraction, respectively. Patients should not see the charts until the test begins. The lens correction from the patient's refraction should be in the trial frame worn by the patient.

All eyes must be tested at 4 meters first, even if the refraction was performed at 1 meter.

The patient should be seated comfortably directly in front of the chart so that the eyes remain at the 4 meter distance. Testing always begins with the right eye. The fellow eye should be occluded with a folded tissue or eye pad lightly taped over the eye behind the trial frame serves as an effective occluder that allows eccentric fixation without inadvertent use of the covered eye. After testing the right eye, occlusion of the right eye should be done BEFORE Chart 2 is put up for testing the left eye.

The patient is asked to read the letters slowly, approximately one letter per second. The patient should be told that only one chance is given to read each letter, but may change their mind before moving to the next letter. If the patient is unsure about the identity of the letter, then the patient should be encouraged to guess.

The patient should begin by reading the top line of the chart and continue reading every letter on each smaller line, from left to right on each line. The patient should be encouraged to continue reading even if making mistakes. Each letter read is counted. The examiner circles every correct letter read and totals each line and the whole column (0 if no letters are correct) on the provided VA worksheet. An X is put through letters read incorrectly. Letters, for which no guess was attempted, are not marked. When a patient reaches a level where he/she cannot guess, the examiner may stop the test, provided that the patient has made errors on previous guesses, which is a clear indication that the best visual acuity has been obtained.

When a patient cannot read at least 20 letters on the chart at 4 meters, the patient is tested at 1 meter. The distance from the patient to the chart should be measured again using the rigid one meter stick. The distance is measured from the outer canthus to the center of the fourth letter (right eye) or the second letter (left eye) of the third line of the chart. The spherical correction in the trial frame should be changed by adding +0.75 to correct for the closer test distance. The patient may fixate eccentrically or turn or shake his/her head to improve visual acuity. Particular care should be taken to make sure the patient does not move forward when testing at 1 meter. The patient should be reminded to blink.

The examiner should not tell the patient if a letter was identified correctly. The patient may be encouraged by neutral comments, such as “good,” “next,” and “OK.”

The examiner should not stand close to the chart during testing. Attention should be focused on the patient and the VA worksheet. If the patient has difficulty locating the next line to read, the examiner may go up to the chart and point briefly to the next line to be read, but then must move away from the chart.

When 20 or more letters are read at 4 meters the visual acuity score for that eye is recorded as the number of letters correct at 4 meters plus 30 (refer to the VA worksheet). The patient gets credit for the 30 letters at 1 meter even though they did not have to read them. Otherwise, the visual acuity score is the number of letters read correctly at 1 meter plus the number, if any, read at 4 meters. If no letters are read correctly at either 4.0 meters or 1 meter, then the visual acuity score is recorded as “0.”

